Official Study Title: *The Effect of Virtual Reality on Pain and Patient Satisfaction in Adults Receiving Genicular Nerve Radiofrequency Ablation*

NCT Number: NCT05468398

Date: April 23, 2025

Study Protocol

Study Title

The Effect of Virtual Reality on Pain and Anxiety in Adults Receiving Genicular Nerve Radiofrequency Ablation

Principal Investigator

[name], MD
Department of Anesthesia and Perioperative Care
University of California, Irvine
Email: [contact]
[contact]

Sponsor

University of California, Irvine

1. Background and Rationale

This study aimed to investigate whether Virtual Reality (VR) therapy could reduce procedural pain and anxiety in adults undergoing genicular nerve radiofrequency ablation (GNRFA). The study utilized the SootheVR system, a medically curated immersive VR device, during the procedure. VR therapy has emerged as a promising non-pharmacologic adjunct for managing procedural discomfort and anxiety.

2. Study Objectives

Primary Objective:

- To evaluate the effect of VR therapy on post-procedural pain levels using the Visual Analog Scale (VAS).

Secondary Objectives:

- To assess pre- and post-procedure anxiety scores.
- To measure patient satisfaction with the procedure.
- To assess provider satisfaction and perception of patient pain.
- To determine the use of additional local anesthetic.

3. Study Design

This was a randomized, non-blinded, single-site interventional study. Participants undergoing GNRFA were randomized to either receive standard care alone or standard care plus VR therapy using the SootheVR headset. Surveys were administered before and after the procedure to collect pain, anxiety, and satisfaction scores. Data were entered via Qualtrics.

4. Eligibility Criteria

Inclusion Criteria:

- Adults \geq 18 years
- Undergoing genicular nerve radiofrequency ablation
- Ability to consent

Exclusion Criteria:

- Need for sedation during procedure
- Cognitive impairment
- Neurological contraindications (e.g., epilepsy)
- Refusal or intolerance to VR headset
- Pregnancy
- Motion sickness, visual/auditory impairments affecting headset use

5. Study Procedures

Participants were screened and consented on the day of the procedure. Baseline pain, anxiety, and prior VR experience were recorded via survey. Participants were then randomized to either VR or control group. Standard GNRFA was performed using fluoroscopy guidance. The VR group used the SootheVR headset during the procedure. Post-procedure, surveys captured outcome data including pain, anxiety, and satisfaction metrics.

6. Statistical Analysis Plan

Data were analyzed using descriptive statistics and comparative tests. Paired t-tests or Wilcoxon signed-rank tests were used to evaluate changes in pain and anxiety scores. Group comparisons were conducted using independent t-tests or Mann-Whitney U tests where applicable. Significance was set at $p < 0.05$.

7. Data Management

Data were entered into Qualtrics and exported to secure institutional drives for analysis. No protected health information was stored outside of secure UCI systems. Only authorized personnel had access to the data. Surveys and raw data were retained for IRB compliance and results reporting.

8. Ethics and Oversight

This study was reviewed and approved by the University of California, Irvine Institutional Review Board (IRB #2020-6207). All participants gave informed consent. Data confidentiality was maintained throughout the study. The study was minimal risk and included monitoring for adverse reactions to VR technology.

9. Study Status

The study has been completed. Enrollment and data collection are finalized. Results analysis is underway and will be submitted to ClinicalTrials.gov.

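### Section 6 ties no between-arm test to the primary pain outcome and plans no baseline adjustment, and the reference period of the pain VAS is not stated

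*Combined protocol and SAP*

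**What the plan says.** Section 1 gives the aim as finding out whether VR "could reduce procedural pain and anxiety in adults undergoing genicular nerve radiofrequency ablation (GNRFA". Section 2 sets the primary objective: "To evaluate the effect of VR therapy on post-procedural pain levels using the Visual Analog Scale (VAS". No recall window or assessment time is attached to it.

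Section 3 describes when scores were taken: "Surveys were administered before and after the procedure to collect pain, anxiety, and satisfaction scores". Section 5 adds the order of events: "Baseline pain, anxiety, and prior VR experience were recorded via survey. Participants were then randomized to either VR or control group". On the intervention it says "The VR group used the SootheVR headset during the procedure", and on outcomes "Post-procedure, surveys captured outcome data including pain, anxiety, and satisfaction metrics".

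Section 6 names pain once: "Paired t-tests or Wilcoxon signed-rank tests were used to evaluate changes in pain and anxiety scores". The next sentence provides for group comparisons by independent t-test or Mann-Whitney test as appropriate. It names no outcome, does not say whether post-scores or changes are compared, and designates no primary test. No covariate-adjusted analysis appears. The significance level is 0.05.

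Other secondary outcomes concern the procedure: patient satisfaction ("To measure patient satisfaction with the procedure"), the provider's view of the patient's pain, and extra local anesthetic. None of these is a patient-reported pain score.

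Section 7 says that surveys and raw data were kept. Section 9 says that data collection is finished and analysis is in progress.

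**The concern.** The trial is randomized, so its evidence about VR lies in the contrast between arms. The only analysis that Section 6 attaches to pain by name compares participants with themselves. Whether it is run within each arm or on everyone together (the section does not say), the change it tests includes whatever both arms share: the ablation, standard care and the passage of time. The comparison that could answer the primary objective is listed, but it is not tied to that objective. The analyst is therefore free to choose the outcome scale, the test, and which result to lead with. A baseline pain score taken before randomization is available, but no adjusted model uses it.

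A second gap affects interpretation. VR was worn during the procedure and the stated aim is procedural pain, but the primary outcome is post-procedural pain with no reference period. If the item asked about current pain, neither a positive nor a null primary result supports a conclusion about pain during the procedure. If it asked about pain during the procedure, a pre/post difference compares two different quantities, because procedural pain could not be rated at baseline.

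**Working it through.** The documents give no sample size, SD, correlation or expected effect, so there is no figure to reproduce. The text was compared section by section. The sizes below rest on assumed inputs.

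**1. Which analysis can isolate VR.** Let the mean pre/post change be *c* in the control arm and *c* + *v* in the VR arm, where *v* is the VR effect. A paired test in the VR arm tests *c* + *v* = 0. A paired test on both arms pooled (equal allocation) tests *c* + *v*/2 = 0. Neither tests *v* = 0. The between-arm comparison does, on post-scores or on changes, because randomization balances baseline in expectation.

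**2. What baseline adjustment would gain.** Let *r* be the baseline/post correlation, with equal SDs σ at both times. Per-participant variances are:

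- post-score: σ²
- change score: 2σ²(1 − *r*)
- ANCOVA residual: σ²(1 − *r*²)

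The ANCOVA variance ratio is therefore 1 − *r*² against post-scores, and (1 − *r*²) / [2(1 − *r*)] = (1 + *r*)/2 against change scores. The equivalent sample-size factor is the reciprocal.

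| assumed r | ratio against post-scores | sample-size factor | ratio against change scores | sample-size factor |
|---|---|---|---|---|
| 0.3 | 1 − 0.09 = 0.91 | 1.10 | 1.3/2 = 0.65 | 1.54 |
| 0.5 | 1 − 0.25 = 0.75 | 1.33 | 1.5/2 = 0.75 | 1.33 |
| 0.7 | 1 − 0.49 = 0.51 | 1.96 | 1.7/2 = 0.85 | 1.18 |

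Neither ratio exceeds 1, so in large samples ANCOVA is no worse than either unadjusted comparison. How much it gains depends on which one Section 6 means.

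**3. What misreading paired tests would cost.** Suppose VR has no effect, the true change is the same in both arms, the arms are independent, and each arm's paired test is significant with probability *p*. The VR arm is then significant and the control arm not with probability *p*(1 − *p*):

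- *p* = 0.05 or 0.95: 0.05 × 0.95 = 0.0475, about 5%
- *p* = 0.2 or 0.8: 0.2 × 0.8 = 16%
- *p* = 0.5: 0.5 × 0.5 = 25%, the maximum

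A simulation of 20,000 trials (assumed: 30 per arm, *r* = 0.5, true change of 0.4 SD in both arms, no VR effect) agrees. Each paired test was significant in 56% of trials, the VR arm alone in 24.7%, and the between-arm t-test in 4.7%.

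**4. What the VAS item measured.** Two features favour current pain: the primary objective's literal wording, and a paired test of change, which presumes the same quantity at both times. Three favour pain during the procedure: the aim in Section 1, the fact that a survey taken afterwards can ask about it, and companion outcomes that concern the procedure. The text does not decide between them.

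**The case against.** Section 6 does list between-group tests, and an unadjusted comparison of randomized arms is valid. Nothing says that a paired result will be presented as the VR effect, so the error in step 3 is hypothetical, and at extreme values of *p* it is only about 5%. The group tests may also have been meant for change scores, in which case baseline is already used. ANCOVA is a gain in efficiency and not a correction of bias. Adding it after data collection in a non-blinded study adds analytic freedom unless it is stated which result carries the conclusion. Finally, even if the item meant current pain, the trial still answers the primary objective as worded.

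Most of this stands, and it limits the point. A reader might infer that the plan has no between-arm comparison, or that it will credit VR with a pre/post change. The documents support neither. A reader might also infer that patients never rated their procedural pain, or that current pain is the likelier meaning of the item. The survey wording is not in the documents, and the clues point both ways.

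What the objection does not remove is that no test is tied to the primary outcome, no adjusted analysis is planned, and the reference period is missing.

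**Conclusion.** The point holds as a gap in how the primary question is analysed and interpreted, and it should be closed before results are submitted. Section 6 does not commit to a between-arm analysis of the VAS, and the one analysis that it links to pain by name cannot isolate VR. These findings, and the missing reference period, rest on the text alone.

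The sizes are conditional. The gain from adjustment depends on an assumed *r*, equal SDs, large-sample behaviour and the comparator, and it may be smaller if the item asked about pain during the procedure, because *r* may then be lower. The error of up to 25% applies only if separate paired tests are read as the VR effect, which the plan does not say. How far the primary result bears on the aim in Section 1 cannot be judged until the survey wording is reported.

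**What to change.** Keep the primary outcome and make three changes.

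1. **Base the VR conclusion on the between-arm comparison of post-procedure VAS.** Fit an ANCOVA with baseline pain as covariate and report the planned unadjusted test beside it, saying whether the t-test or the Mann-Whitney test was used and why. If between-arm results have not been seen, fix and date ANCOVA now as the analysis that carries the conclusion, and disclose that it was added after data collection. If they have been seen, the planned between-arm test carries the conclusion and ANCOVA is labelled post hoc.
2. **Report the paired tests as descriptive only**, and do not interpret them as a VR effect.
3. **State the VAS item's reference period and timing from the retained survey.** If it asked about current pain, limit the primary conclusion to post-procedural pain, leave the aim in Section 1 as written, and acknowledge the gap. If it asked about pain during the procedure, say so and do not read the pre/post difference as a change in one quantity. In either case, the provider's view of pain and extra local anesthetic may be reported as related secondary outcomes, but not as substitutes for a patient's pain score.

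The cost is one look at a retained survey, short wording edits and one extra model on data in hand. The downsides are disclosing a late addition and possibly a narrower conclusion.

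### Could the undated headset-intolerance and sedation exclusions bias the primary VAS comparison, given that Section 6 names no analysis set?

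*Combined protocol and SAP*

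**What the plan says.** Section 4 lists six exclusions and dates none of them. Two could in principle describe something seen only once the procedure has begun: "Refusal or intolerance to VR headset" and "Need for sedation during procedure".

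Section 5 gives the sequence. It opens with "Participants were screened and consented on the day of the procedure", continues with a baseline survey of pain, anxiety and previous VR experience, and then states "Participants were then randomized to either VR or control group". The procedure follows, and the only headset wear described is there: "The VR group used the SootheVR headset during the procedure".

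Section 3 describes the design: "This was a randomized, non-blinded, single-site interventional study". On the between-group analysis, Section 6 says "Group comparisons were conducted using independent t-tests or Mann-Whitney U tests where applicable" and sets the significance level at 0.05. It names no analysis set and gives no rule for patients who take the headset off, are sedated or lack a post-procedure score.

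Section 7 adds "Surveys and raw data were retained for IRB compliance and results reporting". Section 8 mentions monitoring for adverse reactions to VR. Section 9 says that data collection is finished and analysis is in progress.

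**The concern.** Taken literally, an undated exclusion can be applied at any time. The documents describe no trial of the headset before allocation, so intolerance that first appears in use can be seen only in the VR arm. Dropping those patients would thin one arm selectively. If they had more pain than the rest, the VR mean would fall and VR would look better than it is.

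Sedation need is worded as something that happens during the procedure, and staff know the allocation. If VR reduces pain, fewer VR patients might need sedation. Dropping sedated patients would then take more high-pain patients out of the control arm and shrink a real effect.

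The primary objective, post-procedural pain on the VAS, rests on this comparison, and Section 6 contains no analyse-as-randomised statement that would rule such exclusions out.

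**Working it through.** **Inputs.** From the documents: alpha 0.05 and an independent t-test as one of the two between-group options (Section 6). The test is taken as two-sided because sidedness is not stated. The documents give no sample size, SD, target difference, intolerance rate or sedation rate, so there is no planned figure to reproduce. Everything below the first step rests on assumptions.

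**Step 1: what the text implies about timing.**
- The two lines sit under eligibility, so they are rules for entering the study.
- Section 5 puts screening first and randomisation after it.
- Refusal, and intolerance known from history, can be judged before allocation. Section 5 records previous VR experience at baseline, and Section 4 separately excludes motion sickness and sensory impairments that affect headset use.
- Section 8's monitoring is a safety statement and says nothing about removing anyone from the analysis.
- No passage directs or reports a removal after randomisation.

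On this reading the exclusion bias is zero.

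**Step 2: headset-intolerant patients dropped from the VR arm anyway.** Let a share f of the VR arm be dropped, with mean pain D SD above the remainder. The full-arm mean equals the remainder's mean plus f × D, so dropping them shifts the comparison by f × D in favour of VR. With n controls, n(1−f) VR patients and no true effect, the t statistic has noncentrality f × D / √(1/n + 1/[n(1−f)]) on n + n(1−f) − 2 degrees of freedom.

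Example: n = 50, f = 0.20, D = 1. The shift is 0.20 SD, √(1/50 + 1/40) = 0.2121, the noncentrality is 0.20/0.2121 = 0.943 on 88 df, and the two-sided rejection rate is 15.4%.

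| f | D | Shift (SD) | False-positive rate, 50 per arm | False-positive rate, 20 per arm |
|---|---|---|---|---|
| 10% | 0.5 | 0.05 | 5.7% | 5.3% |
| 10% | 1 | 0.10 | 7.7% | 6.0% |
| 20% | 0.5 | 0.10 | 7.5% | 6.0% |
| 20% | 1 | 0.20 | 15.4% | 8.9% |
| 10% or 20% | 0 | 0 | 5.0% | 5.0% |

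If D is negative, the shift goes against VR. A second model, with a latent intolerance score correlated 0.3–0.5 with pain and 10–20% dropped, gave shifts of 0.06–0.17 SD and simulated error rates of 5.8–13.3% at 50 per arm. The two models agree on the order of size.

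**Step 3: sedated patients dropped from both arms.** Let a share q of controls be sedated, with sedation propensity correlated r with pain, and let the true VR effect be e = 0.5 SD. Write c for the standard normal (1−q) quantile and L = φ/Φ. The observed effect is e − r[L(c) − L(c+d)], where d is the shift in sedation propensity under VR, taken as r × e or e.
- q = 10%, r = 0.3–0.5: 2.4–11.0% of the effect is lost.
- q = 20%, r = 0.3–0.5: 3.6–17.2% is lost.
- e = 0 with one threshold for both arms: d = 0, the bracket vanishes and there is no bias.

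The sedation limb therefore cannot create a false effect under a common threshold. It can only dilute a true one.

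**The case for a change.** The strongest case for acting is that the gap is real and closing it is cheap. A patient who has never worn the headset can refuse it but cannot yet show new intolerance, so screening does not fully cover that criterion. The trial is unblinded, one-sided removal is a standard way for randomisation to be undone, and neither Section 4 nor Section 6 forbids it. The data are retained and analysis is said to be in progress, so one sentence on the analysis set and a table by arm would settle the matter.

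Some of this stands. Section 6 is silent on the analysis set, and intolerance first seen in use is a credible one-sided route. But it shows only what could happen if someone departed from the ordinary meaning of an entry criterion. Bias also requires the removed patients' pain to differ from the others', which the documents do not show. The 15.4% figure is the worst corner of an assumed grid. For sedation, a difference between arms is plausible but not shown.

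The remedy would gain little. A sentence added to Section 6 now would postdate data collection, so it could not serve as pre-specification. Imputation with a tipping-point analysis would answer a missing-data problem that the documents do not report.

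**Conclusion.** No change to the plan is called for. Its natural reading, with eligibility settled at screening and patients then randomised and compared by assigned arm, gives a comparison free of this bias. What is absent is a written analysis set, a gap that analysts fill sensibly by keeping randomised patients in their arm. Numbers randomised, excluded and analysed by arm, with reasons, belong in any ordinary results report and would show whether the question ever arose.

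The residual risk is conditional. It needs patients to have been dropped after randomisation and, for the headset criterion, their pain to have differed from the rest. If 10–20% of the VR arm were dropped with pain 0.5–1 SD higher, the shift would be 0.05–0.20 SD in favour of VR. The false-positive rate would then be 5.7–15.4% at 50 per arm or 5.3–8.9% at 20 per arm. The sedation criterion is the weaker limb: it gives no bias if VR has no effect and one threshold applies to both arms. The shares, pain differences, correlations, 0.5 SD effect and arm sizes are all assumptions, because the documents supply none of them.

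### Section 6 compares the arms only with unadjusted tests, although baseline pain and anxiety were recorded before randomisation; the likely cost is precision, not validity

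*Combined protocol and SAP*

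**What the plan says.** Section 6 has one sentence on comparing arms: "Group comparisons were conducted using independent t-tests or Mann-Whitney U tests where applicable". It does not name an outcome, say whether post-procedure or change scores are compared, mention a covariate, or mark a test as primary. Pain and anxiety appear only in the sentence before it, which concerns within-patient change: "Paired t-tests or Wilcoxon signed-rank tests were used to evaluate changes in pain and anxiety scores".

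Other sections fill part of the gap. Section 2 gives the primary objective as "To evaluate the effect of VR therapy on post-procedural pain levels using the Visual Analog Scale (VAS"), which points to the post-procedure score. For anxiety it says only "To assess pre- and post-procedure anxiety scores". Section 5 gives the order of events: "Baseline pain, anxiety, and prior VR experience were recorded via survey. Participants were then randomized to either VR or control group". Section 9 says that data collection is finalised and that "Results analysis is underway and will be submitted to ClinicalTrials.gov". No baseline-adjusted model appears anywhere.

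**The concern.** A baseline measured before randomisation is a legitimate covariate. When it correlates with the outcome, adjusting for it removes noise from the treatment contrast at no cost in patients. The two unadjusted readings treat it differently: a post-score test ignores it, and a change-score test subtracts it in full whatever the correlation. Which of the two is more precise depends on a correlation that the documents do not give.

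For pain, where Section 2 points to the post score, the question is how much precision is lost by ignoring baseline. For anxiety there is also an open choice between two analyses that can differ clearly in power on the same data. The precision of the VR estimate is at stake, and so is clarity about which result concerns VR, because the only tests tied by name to pain and anxiety are within-patient ones.

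**Working it through.** The plan gives no sample size, power, SD or correlation, so it has no figure to reproduce. All inputs below are assumptions: 1:1 allocation, two-sided 5% tests, baseline-to-post correlation ρ of 0.3/0.5/0.7, 20 per arm (N = 40) and, at first, equal baseline and post SDs.

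**Step 1: large-sample variance of the arm difference**, with the post-score test set to 1. The change score has 2(1−ρ) and the adjusted model 1−ρ². CI-width ratios are therefore √(1−ρ²) against post and √((1+ρ)/2) against change.

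| ρ | Post | Change | Adjusted | Width, adjusted/post | Width, adjusted/change |
|---|---|---|---|---|---|
| 0.3 | 1 | 1.40 | 0.91 | 0.954 | 0.806 |
| 0.5 | 1 | 1.00 | 0.75 | 0.866 | 0.866 |
| 0.7 | 1 | 0.60 | 0.51 | 0.714 | 0.922 |

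**Step 2: cost of estimating the slope.** The adjusted variance is inflated by about 1+1/(N−4). At N = 40 this multiplies the width by √(1+1/36) = 1.014. Adjusted/post becomes 0.967/0.878/0.724 and adjusted/change 0.817/0.878/0.935. Simulation (40,000 normal-data trials per case) gives 0.968/0.878/0.725 and 0.818/0.879/0.935.

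**Step 3: when adjustment loses to the post score.** At ρ = 0 the adjusted CI is 1.4% wider at 20 per arm. Break-even is where (1−ρ²)(1+1/(N−4)) = 1, that is ρ = 1/√(N−3). This gives 0.19 at 15 per arm (1/√27), 0.16 at 20 (1/√37) and 0.13 at 30 (1/√57). Simulated mean CI width agrees: about 0.20, 0.17 and 0.13.

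**Step 4: unequal SDs.** Let k be baseline SD divided by post SD. The change-score variance is 1 + k² − 2ρk = (1−ρ²) + (k−ρ)². In large samples this is never below the adjusted variance, and the two are equal when k = ρ. In that case only the small-sample cost remains: the adjusted CI is 1.4% wider than the change-score CI at 20 per arm and 2.0% wider at 15. At ρ = 0.7 and 15 per arm, power for an effect of 0.7 SD is 72% adjusted and 74% for change.

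**Step 5: power** at 20 per arm, effect 0.7 SD, equal SDs, ρ = 0.3/0.5/0.7.
- Post score: about 58%.
- Change score: 44.5/57.8/79.4%.
- Adjusted: 60.8/69.0/84.5%. At ρ = 0 it has 56.4%.

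**Step 6: bounded scale.** Scores were rounded and clipped to 0-10 (baseline mean 5, post mean 3, SD 2.5, effect 1.75 points), 20 per arm. Power is about 54% for the post t-test, 53% for Mann-Whitney on post scores, 35/45/62% for the change t-test and 56/63/77% adjusted. The adjusted model's false-positive rate is 4.8-5.3% at 15-50 per arm.

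**The case against.** The strongest case against acting is that Section 2 already points to post-procedure pain, the listed tests are valid, and the benefit of adjustment rests on an assumed correlation. Section 5 does not say what baseline pain refers to, and nothing in the documents favours a correlation of 0.7 over 0.3. At 0.3 the gain over the post-score test is about 3% in CI width and three points of power. In addition, making an unlisted model primary after data collection, in a non-blinded study, creates a new analyst choice.

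Most of this stands. It limits the size of the claim and shapes the fix, but it does not remove the point: the baseline is already collected, the worst cost of using it is small, and Section 6 still does not carry over the contrast that Section 2 implies.

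A reader might infer four stronger things, none of which the documents support.
- *The listed tests are biased.* They are not; randomisation makes both the post and the change comparison valid.
- *Post versus change is equally open for pain.* Section 2's wording largely settles it for the primary outcome. The change-score figures bear mainly on anxiety.
- *Adjustment always wins at correlations 0.3-0.7.* That needs a condition on the SDs: Step 4 shows a slight loss to the change score when the SD ratio equals the correlation.
- *The paired tests, or the better of several p-values, will serve as evidence for VR.* The plan states neither use and gives between-group tests in a separate sentence, so false-positive rates for such conduct carry no weight here.

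**Conclusion.** The point holds as one of efficiency and clarity. Section 6 leaves a pre-randomisation baseline out of its stated between-arm methods, except in so far as an unstated change-score test would use it, and ties its between-arm test to no outcome.

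Under the assumptions in the working (equal SDs, 20 per arm), the adjusted CI is about 3/12/28% narrower than the post-score CI at correlations 0.3/0.5/0.7, which is the relevant comparison for pain. Against a change-score analysis, which remains possible for anxiety, it is 18/12/6% narrower. The downside is a CI about 1-2% wider, in the two situations of Steps 3 and 4.

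Confidence is high on the gap in the text. The size of the benefit is uncertain, because it depends on a correlation and an SD ratio that only the trial data can supply. The plan should be changed, but results from the listed tests would not be invalid without the change.

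**What to change.** In Section 6, state the following.
- The VR-minus-control difference in post-procedure VAS pain is estimated from a linear model with randomised arm and baseline pain, with a 95% CI.
- Anxiety is analysed in the same way, with baseline anxiety.
- The listed unadjusted test of post-procedure scores is always reported beside the adjusted result.
- Paired pre/post results are given per arm as descriptive only.

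Date the change, disclose that it was made after data collection, and state whether arm-level results had been seen. If they had, label the adjusted analysis as supportive.

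The cost is a wording change and a re-run on scores already collected: no patients and no new data. The adjusted analysis must be reported as specified after data collection, and its interval may turn out 1-2% wider if baseline proves uninformative.

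### Section 6 links no test to the primary objective: its only sentence on pain uses paired tests with no VR-versus-control contrast, and its between-arm tests name no outcome and state no use of baseline pain

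*Combined protocol and SAP*

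**What the plan says.** Section 2 gives the primary objective as "To evaluate the effect of VR therapy on post-procedural pain levels using the Visual Analog Scale (VAS". Among the secondary objectives is "To assess pre- and post-procedure anxiety scores". Section 3 sets the comparison: "Participants undergoing GNRFA were randomized to either receive standard care alone or standard care plus VR therapy using the SootheVR headset". It adds that "Surveys were administered before and after the procedure to collect pain, anxiety, and satisfaction scores". Section 5 says "Baseline pain, anxiety, and prior VR experience were recorded via survey", and places randomization after that step. It does not give the scale of the baseline pain score.

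Section 6 has four sentences. The first is general: "Data were analyzed using descriptive statistics and comparative tests". The second is the only one that names pain: "Paired t-tests or Wilcoxon signed-rank tests were used to evaluate changes in pain and anxiety scores". The third covers comparisons between groups: "Group comparisons were conducted using independent t-tests or Mann-Whitney U tests where applicable". The fourth sets the significance level at 0.05 without saying whether tests are one- or two-sided. No primary analysis is designated and no covariate-adjusted model is mentioned. Section 9 reports that data collection has closed and that analysis is in progress.

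**The concern.** The primary question needs a contrast in pain between the randomized arms. The tests that Section 6 attaches to pain are within-participant. They suit a before/after description, such as the secondary objective on anxiety, but they cannot estimate what VR adds to standard care. The tests that could answer the question are attached to no outcome, time point, or choice of post score or change.

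Two things are at stake.

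- **The missing link.** A before/after change in pain could be reported as the answer to the primary objective although it does not compare VR with control. Pain usually differs before and after a procedure for reasons shared by both arms.
- **Precision.** A pain score collected before randomization is a legitimate covariate, and the plan states no use of it. If it predicts post-procedural pain, the confidence interval for the VR effect will be wider than necessary.

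**Working it through.** **No figure to reproduce.** The documents give no sample size, power, SD, effect size, correlation or allocation ratio. Every numerical input below is an assumption.

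**1. Matching tests to the objective.**

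| Element | Primary objective needs | Paired sentence | Between-arm sentence |
|---|---|---|---|
| Outcome | Post-procedural VAS pain | Change in pain and anxiety | Not named |
| Contrast | VR versus control | None | Between groups |
| Baseline pain | Optional covariate | Used in the change | No use stated |

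Neither sentence alone specifies the primary analysis. Read with Sections 2 and 3, the natural reading is an unadjusted t or Mann-Whitney test of post-procedural VAS, but the text does not say so.

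**2. Precision.** Let r be the correlation of baseline with post-procedural pain, with equal SDs. Relative to the post score alone (variance 1), a change score has variance 2(1 − r) and ANCOVA has 1 − r².

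| r | ANCOVA variance | Reduction vs post score | CI narrower by 1 − √(1 − r²) | Reduction vs change, (1 − r)/2 |
|---|---|---|---|---|
| 0.3 | 0.91 | 9% | 5% | 35% |
| 0.5 | 0.75 | 25% | 13% | 25% |
| 0.7 | 0.51 | 49% | 29% | 15% |

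The gain was also simulated on bounded and skewed scales: 0–10 roughly symmetric, 0–10 skewed and 0–100 skewed, with 20, 30 or 50 per arm and latent r of 0.3, 0.5 or 0.7 (27 settings, 10,000 no-effect trials each). The reduction versus post score was 3–8% at r = 0.3 and 38–46% at r = 0.7.

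**3. Power, for 30 per arm, a 0.6 SD effect and two-sided 0.05.**

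- Unadjusted: noncentrality 0.6 × √(30/2) = 2.324 on 58 df, power 62.8%.
- ANCOVA: noncentrality 2.324/√[(1 − r²)(1 + 1/56)] on 57 df. The factor 1 + 1/56 allows for chance baseline imbalance.
- ANCOVA power is 62.0% at r = 0, 62.4% at 0.1, 63.7% at 0.2, 66% at 0.3, 74% at 0.5 and 89% at 0.7.
- The largest loss is 62.8 − 62.0 = 0.8 points, at r = 0.

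**4. Type I error.** In the same 27 settings, a single between-arm t or rank test fixed in advance gave 4.5–5.5%, and ANCOVA 4.7–5.4%. Choosing t or rank by a normality test gave 4.4–5.5%. Higher rates arise only if the analysis is picked by its result: 8.3–10.1% for post score or change, 6.0–8.7% for the better of unadjusted t and ANCOVA.

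**5. Paired tests read arm by arm.** Suppose both arms have the same true change. The chance that VR is significant and control is not is p_VR × (1 − p_C), where p is the power of each arm's paired test. With equal arms p_VR = p_C, and the maximum is 0.5 × 0.5 = 25%. With unequal arms it can be higher: 31% at 45 VR/35 control, 42% at 40/20 and 48% at 50/20.

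**The case against.** The strongest reply is that Section 6 does list between-arm tests, and that Sections 2, 3 and 6 together point to an unadjusted comparison of post-procedural VAS. That comparison is valid in a randomized trial, so preferring ANCOVA is a matter of efficiency and not the correction of an error. This stands: the baseline point concerns precision, not bias.

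The precision gain is also not assured. Section 1 is concerned with pain from the procedure, which a score taken beforehand may predict weakly, and the baseline scale is not stated. At correlations near 0 to 0.1 the gain disappears. This stands too, and makes the gain conditional.

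A third objection is that making ANCOVA decisive now would move the decision to a method chosen after data collection, perhaps after the listed tests were run. Section 6 is in the past tense, so this is a fair warning, and it limits the fix.

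A reader might infer more than the text supports:

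- **That no between-arm test is planned.** One is listed; it is simply not tied to pain.
- **That baseline pain is ignored.** The plan states no use of it in the between-arm tests, but does not exclude applying those tests to change scores, which would use it.
- **That the type I error is inflated.** The higher rates need a choice driven by results, and nothing in the documents says this was done.
- **That arm-by-arm paired tests were meant as evidence for VR.** Section 6 does not say so.

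**Conclusion.** The concern holds as a gap in specification with a conditional cost in precision. No test in Section 6 is linked to the primary objective, and the only tests attached to pain cannot estimate the VR effect. That much rests on the text alone.

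The size of the precision cost rests on assumed correlations and equal SDs: none to speak of if baseline pain is nearly uncorrelated with post-procedural pain, and about half the variance at a correlation of 0.7. The documents do not show where this trial lies in that range. They do not support a claim of bias or of an inflated error rate. The point should be addressed before results are posted, with medium confidence in its practical importance.

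**What to change.** - State in Section 6 that the primary objective is answered by the between-arm difference in post-procedural VAS pain, two-sided 0.05, with a 95% CI.
- Report together the ANCOVA estimate adjusted for the recorded baseline pain score and the unadjusted test already listed. Name one of them in advance as carrying the 0.05 decision.
- Let ANCOVA carry it only if no earlier plan named another analysis and the between-arm pain results have not been seen. Otherwise keep the listed unadjusted between-arm test as primary and label ANCOVA supportive and post hoc. If a dated earlier plan named a different primary analysis, cite it and keep that one.
- Unless a dated earlier plan exists, disclose that the specification was made after data collection closed.
- Label the paired tests descriptive and not evidence of a VR effect, and change-score comparisons as sensitivity analyses.
- Confirm the scale of the baseline pain score. As a covariate it need not match the outcome scale.

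**Cost.** No new data if the baseline score is usable, and one additional model. The downside is that the ANCOVA may be post hoc, its benefit depends on the baseline score, and rewording cannot restore prespecification.
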